9.5.5 Time to First Achievement of PASI-50

The time to first achievement of the PASI-50 will be analysed using a nonparametric survival analysis for interval-censored data. The expectation-maximisation iterative complex minorant (EMICM) method for iterative computation of the nonparametric maximum likelihood estimator for the survival function ([Wellner and Zhan 1997](#)) will be used.

Treatment will consist of 4 levels or 6 levels based on the appropriateness of the placebo pooling strategy as per the main analytical approach for the primary analysis.

The number and proportion of participants who meet the PASI-50 at least once during the study will be presented. Where calculable, the time to 25% and 50% of participants with PASI-50 will be displayed with its 95% confidence interval. A generalised log-rank test will be used to compare each active dose with placebo and the p-value for treatment difference will also be presented.

A figure showing the estimated survival curves of each treatment group will also be presented.

9.5.6 Partial Relapse, Relapse and Rebound

The following endpoints will be summarised by treatment group and visit in the

- Week 16 responders population:
 - Cumulative incidence of partial relapse at Weeks 20, 24, 28, and 40
 - Cumulative incidence of complete relapse at Weeks 20, 24, 28, and 40
- mITT population:
 - Cumulative incidence of rebound at Weeks 20, 24, 28, and 40

These summary tables will include the number of participants meeting the criteria for the endpoint, and the number of participants 'at risk' of meeting the criteria (the denominator for the cumulative incidence i.e. excluding any participants with a missing status for that endpoint).

For each endpoint, the cumulative incidences for each treatment group will be plotted against time (Week 20 to Week 40) as bars (with an 'error bar' for the corresponding 95% CI).

No inferential analysis of relapse or rebound will be carried out.

Table 6 Intercurrent Event Strategies for Partial Relapse, Relapse and Rebound Endpoints

Endpoint	Intercurrent event	Strategy to account for intercurrent event
Partial Relapse and (Complete) Relapse	Starting a new psoriasis treatment	Composite Starting a new psoriasis treatment is part of the endpoint definition

Endpoint	Intercurrent event	Strategy to account for intercurrent event
Rebound	Starting a new psoriasis treatment	
While in the period following cessation of study treatment, without taking a new psoriasis treatment (analogous to While on treatment)
 
Rebound status will be considered missing from 4 days after the day a new psoriasis treatment is started, onwards, and will not be counted in the denominator during calculation of cumulative incidences

Note that, according to the study design, starting a new psoriasis treatment (synonymous with study treatment failure) should result in a subject completing a PASI questionnaire at an unscheduled Follow-up (Part A)/Early Withdrawal (Part B) visit within 72 hours and then being withdrawn from the study. The above strategies for dealing with the intercurrent event of starting a new psoriasis treatment are included to cover the possibility of a protocol deviation occurring whereby a participant is not withdrawn from the study within 72 hours following the start of a new psoriasis treatment, and to clarify the estimand for rebound.

Once a participant has met the criteria for partial relapse, relapse or rebound (see [Section 5.3.3.2](#)) they will be counted as having met those criteria at the current (if a PASI criterion at Week 20 or later) or next, and all subsequent, scheduled visits where these endpoints are analysed (Week 20, 24, 28, and 40).

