7.6 Statistical Analysis Methodology

Statistical analysis will be performed using SAS software Version 9.3 or later.

In addition to the inferential analyses described in Sections 7.6.1 and 7.6.2, descriptive statistics will be provided to summarize all endpoints by treatment group.

Continuous variables will be summarized using the mean, standard deviation, median, minimum value, and maximum value. Categorical variables will be summarized using frequency counts and percentages. Time-to-event variables will be summarized using Kaplan-Meier estimates of the proportion of participants with the event at each visit. Data will be listed in data listings.

Details of the statistical analyses, methods, and data conventions will be described in the SAP.

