7.3 Missing Data

Missing efficacy data such as individual item scores will be dealt with as detailed in [Section 5.3.3](#). Otherwise, no imputation of missing efficacy data will be performed, and the use of mixed models will account for missing data.

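### Relapse and rebound incidence in SAP 9.5.6 keeps past events but drops event-free leavers, so it can rise with no new event

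*SAP*

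**What the plan says.** SAP 9.5.6 reports partial and complete relapse (Week 16 responders) and rebound (mITT) at Weeks 20, 24, 28 and 40, by treatment group, with 95% CI bars and no inferential analysis. Four rules determine the figure.

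- **Numerator.** A participant who meets the criteria counts as an event at that or the next visit "and all subsequent, scheduled visits where these endpoints are analysed (Week 20, 24, 28, and 40").
- **Denominator.** The number at risk is "the denominator for the cumulative incidence i.e. excluding any participants with a missing status for that endpoint".
- **Missing data.** SAP 7.3 states that, apart from item-level scoring rules, "no imputation of missing efficacy data will be performed".
- **New psoriasis treatment (Table 6).** For partial and complete relapse, "Starting a new psoriasis treatment is part of the endpoint definition". For rebound, "Rebound status will be considered missing from 4 days after the day a new psoriasis treatment is started, onwards", and such a participant "will not be counted in the denominator during calculation of cumulative incidences".

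Protocol Table 7-1 gives the summary measure for all three endpoints as a proportion of participants at each visit. Neither document specifies a censoring-adjusted estimate for them.

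**The concern.** Carrying events forward is sensible: someone who has rebounded need not attend Visits 12 and 13 (Protocol Table 6-2), so the event must be kept without further data. The difficulty is the denominator it is paired with. Event-free participants count only while their status is known, whereas participants with an event count permanently. The ratio therefore discards the event-free follow-up of everyone who left, and it can increase between visits at which nothing happened.

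Relapse and rebound after stopping treatment is a secondary objective and the purpose of Part B. A reader will compare the arms' bars over time. If one arm loses more event-free participants than another, or for rebound has more of them switching, the bars will separate even when the event histories are the same.

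**Working it through.** The documents give no expected event count and no dropout rate after Week 16, so there is no stated figure to reproduce. The event and leaver counts below are assumptions. The arm size of 50 is from SAP 6.

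**Formula.** Let E be the events so far, n the starting number, and d the event-free participants whose status has become missing. The SAP figure is E / (E + event-free still observed) = E / (n − d). This exceeds E / n whenever E ≥ 1 and d ≥ 1. With E = 0 it stays at 0%.

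**Two arms with identical events.** Each has n = 50, with 4 events by Week 20 and none later, leaving 46 event-free. Arm A loses 8 event-free participants before Week 24 and 7 more before Week 28. Arm B loses 3 and then 2.

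| | Week 20 | Week 24 | Week 28 |
|---|---|---|---|
| SAP rule, arm A | 4/50 = 8.0% | 4/(4+38) = 4/42 = 9.5% | 4/(4+31) = 4/35 = 11.4% |
| SAP rule, arm B | 4/50 = 8.0% | 4/(4+43) = 4/47 = 8.5% | 4/(4+41) = 4/45 = 8.9% |
| Kaplan-Meier, either arm | 8.0% | 8.0% | 8.0% |

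Kaplan-Meier for arm A is 1 − (46/50)(38/38)(31/31) = 8.0%. The Week 28 gap under the SAP rule, 11.4 − 8.9 = 2.5 points, comes only from the losses. For rebound, if the losses are switches treated as a competing event, the cumulative incidence function also stays at 4/50 = 8.0%.

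**Relapse.** Take 20 responders with 4 events at Week 20 and 2 event-free leavers before each later visit. The SAP rule gives 4/20, 4/18, 4/16, 4/14 = 20.0%, 22.2%, 25.0%, 28.6%. Kaplan-Meier gives 20.0% throughout.

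**Events that continue, with random leaving.** A simulation of 200,000 participants over four visits used a 10% event risk per visit, so the true Week 40 incidence is 1 − 0.9⁴ = 34.4%. With 5%, 10% and 20% non-informative leaving per visit, the SAP rule gave 36.2%, 38.6% and 43.6%. Kaplan-Meier gave 34.3% to 34.5%. The excess therefore does not need informative dropout.

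**Rebound followed by a switch.** The carry-forward rule keeps this participant as an event. Table 6 makes the status missing and removes the participant. The SAP does not say which prevails. If Table 6 does, and 2 of arm A's 4 rebounders switch before Week 24, the Week 24 figure is 2/(50 − 8 − 2) = 2/40 = 5.0%, below 8.0%.

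**The case against.** The strongest reply is that these are descriptive summaries with the event count and number at risk already shown, so a reader can see the denominator shrink. The losses in arm A are also generous: 15 of 46 event-free participants is 33% in eight weeks, while the only documented rate is at most 15% stopping treatment over 16 weeks. With 8 leavers the shift is 8.0% to 9.5%, small against an exact 95% CI of 2.2% to 19.2% for 4/50. All of that stands and limits the consequence. It does not make the ratio a cumulative incidence.

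Three stronger readings are tempting and are not supported.

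- **Undeclared departure from the protocol.** Protocol 7.6 says "Time-to-event variables will be summarized using Kaplan-Meier estimates of the proportion of participants with the event at each visit", and a reader might infer that the SAP abandoned this without listing it in its Table 8. But the endpoint-specific text in Protocol Table 7-1 asks for a proportion at each visit, and the endpoint framed as time-to-event is time to first PASI-50. A departure is not established.
- **Switching removes participants for every endpoint.** It does so for rebound only. Under partial and complete relapse a switch is counted as an event.
- **Rebound is certain to be overstated.** The clash between Table 6 and the carry-forward rule can push the figure down, as shown. If leavers are mainly those who are worsening, unseen later events would also work the other way. The overstatement is relative to a censoring-adjusted estimate, and Kaplan-Meier itself assumes non-informative censoring.

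**Conclusion.** The rule is wrong as written for a quantity called cumulative incidence. For partial relapse, relapse and rebound, once at least one event has occurred the figure rises with each event-free loss. For rebound, event-free starters of new psoriasis treatment add to this, provided earlier rebounds stay counted. That removal also sits badly with the strategy Table 6 names, follow-up up to a new treatment: a participant who switches without rebound has a known outcome for that period.

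The size depends on losses the documents do not predict. With 4 events in 50 it is 1.5 points for 8 losses and 3.4 points for 15. The conclusion assumes that an event-free leaver's status is missing at later visits, which follows from the no-imputation rule although the SAP does not define missing status. The primary analysis is not affected. Who attends Week 40, and what that means for rebound there, is a separate question.

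**What to change.** In SAP 9.5.6:

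1. For partial and complete relapse at Weeks 20, 24, 28 and 40, report Kaplan-Meier 1 − S, or the interval-censored estimator already used in SAP 9.5.5, since PASI events are detected only at visits. Censor at the last PASI and state the non-informative censoring assumption. The result is still a proportion at each visit, as Protocol Table 7-1 asks.
2. For rebound, use a cumulative incidence function with start of a new psoriasis treatment as a competing event. Show the number of switchers beside the number at risk already planned.
3. State that a rebound occurring before a switch stays counted, which resolves the conflict between Table 6 and the carry-forward rule.
4. Define missing status at each visit.

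The cost is SAP wording and standard procedures, with no new data. The analysis becomes slightly more complex, and the reported incidences may be lower.

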9.6 Exploratory Efficacy Analyses

9.6.1 Exploratory Efficacy Endpoints

The following exploratory endpoints will be summarised using statistics appropriate to the endpoint as described in [Section 9](#):

- Percentage of participants achieving PASI-50, PASI-75, PASI-90, and PASI-100 at Weeks 4, 8, and 12
- Percentage of participants achieving PGA of 0 or 1 with a ≥ 2 -point improvement at Weeks 4, 8, and 12
- Percentage of participants achieving PGA of 0 at Weeks 4, 8, and 12
- Percentage of participants achieving PGA of 0 or 1 at Weeks 4, 8, 12, and 16.
- Mean percentage change from baseline in BSA at Weeks 4, 8, 12, and 16.
- Mean change from baseline in BSA at Weeks 4, 8, 12, and 16.
- Percentage of participants achieving BSA<3% and BSA-75 at Weeks 4, 8, 12, and 16.
- Mean change from baseline in PSI quality of life total and itch scores at Weeks 12 and 16

- Mean percentage change from baseline in PSI quality of life total and itch scores at Weeks 12 and 16
- Mean change from baseline in Pain and Fatigue scores at Weeks 4, 8, 12, and 16
- Mean percentage change from baseline in Pain and Fatigue scores at Weeks 4, 8, 12, and 16
- Mean change from baseline in fasting blood glucose and fasting lipid panel at Weeks 8 and 16
- Mean duration of remission in participants who achieve PASI-100
- Mean duration of treatment success in participants who achieve PASI-50
- Mean duration of therapeutic effect in participants after cessation of study treatment

Note that if a participant has a zero score for any of the continuous measures (PSI score, Pain/Fatigue VAS or Bodily pain/Vitality SF-36 scores) at baseline, that participant will be excluded from any of the percentage change from baseline summaries and analyses as the percentage change from baseline cannot be calculated.

In addition to the summary statistics as described in [Section 9](#), response endpoints will also have 95% CIs presented for percentage of participants responding.

9.6.2 Indirect Comparisons with Apremilast

Adjusted indirect comparisons, pivoted around placebo, will be made with the Week 16 results and those from two studies in Apremilast in mild/moderate or moderate participants.

Only efficacy endpoints which were specified as primary or secondary endpoints in both this study and the comparator study will be assessed.

All indirect comparisons and their confidence intervals will be considered descriptive only. No p-values will be calculated.

Each active dose of EDP1815 will be independently compared to Apremilast.

All data for the comparator studies will be taken from the published results for the study available on the clinicaltrials.gov website.

9.6.2.1 Binary (Response) Endpoints

For binary endpoints (e.g. PASI-50), the indirect comparison will be based on the unadjusted relative risk (RR) statistics re-calculated from the number of participants in each treatment/trial with the relevant endpoint at Week 16. Participants with missing data at Week 16 will have their last observed value before Week 16 carried forward.

N_A = number of participants evaluated on active treatment

N_P = number of participants evaluated on placebo treatment

n_A = number of participants with event on active treatment

n_P = number of participants with event on placebo treatment

$$\text{Relative risk (RR)} = \frac{n_A/N_A}{n_P/N_P}$$

$$\text{SE}(\log \text{RR}) = \sqrt{\left(\frac{1-n_A}{n_A N_A} + \frac{1-n_P}{n_P N_P}\right)}$$

$$\text{RR for Indirect Comparison (RR}_{\text{Indirect}}\text{)} = \frac{\text{RR}_{\text{EDP1815}}}{\text{RR}_{\text{Apremilast}}}$$

$$\text{SE}(\log \text{RR}) \text{ for indirect comparison} = \sqrt{\left[\text{SE}(\log \text{RR}_{\text{EDP1815}})^2 + \text{SE}(\log \text{RR}_{\text{Apremilast}})^2\right]}$$

$$95\% \text{ CI for RR for indirect Comparison} = \exp(\log \text{RR}_{\text{Indirect}} \pm 1.96 \times \text{SE}(\log \text{RR}_{\text{Indirect}}))$$

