5.3.3.11 SF-36 Bodily Pain and Vitality Scores

The SF-36 bodily pain and vitality scores will be calculated using the algorithms provided by the RAND corporation as detailed in [Section 21](#).

The SF-36 bodily pain score will be the average of the two question scores for pain and will be calculated if at least one of the two questions have been answered.

The SF-36 vitality score will be the average of the four question scores for vitality/energy and will be calculated if at least two of the two questions have been answered.

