9.6.2.4 Apremilast ADVANCE study (NCT03721172)

The ADVANCE study was performed in a population of mild/moderate participants. The criteria specified for PGA, BSA or PASI for recruitment into this study were broadly similar to those for this study, therefore the results from the full mITT population will be used for comparison.

The following endpoints will be compared at Week 16:

- Achievement of PGA score of 0 or 1 with ≥ 2 point reduction from baseline (binary)
- Change from baseline in PASI score (continuous)

It should be noted that at the time of writing this SAP, the results were not yet available on clinicaltrials.gov for this study. This analysis will only be performed if these results are published prior to DB lock for this study.

10 Safety Analyses

The Safety population will be used for all summaries of Safety. All safety endpoints will be listed.

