- 4 = Moderate
- 5 = Severe
- 6 = Very severe

The Q21 score = $100 * [(6-x)/5]$ where x=1-6 is the Q21 item value as above.

Q22: During the past 4 weeks, how much did pain interfere with your normal work (including both work outside the home and housework)?

- 1 = Not at all
- 2 = A little bit
- 3 = Moderately
- 4 = Quite a bit
- 5 = Extremely

The Q22 score = $100 * [(5-x)/4]$ where x=1-5 is the Q22 item value as above.

The SF-36 bodily pain score is the average of the Q21 and Q22 scores. If at least one of the two questions have been answered, the SF-36 bodily pain score will be calculated.

Vitality score

The vitality score will be calculated from questions 23, 27, 29 and 31 of the SF-36 questionnaire:

How much of the time during the past 4 weeks...

Q23: Did you feel full of pep?

Q27: Did you have a lot of energy?

Q29: Did you feel worn out?

Q31: Did you feel tired?

Each question has possible answers (x):

- 1 = All of the time
- 2 = Most of the time
- 3 = A good bit of the time
- 4 = Some of the time
- 5 = A little of the time
- 6 = None of the time

The Q23 score = $100*[(6-x)/5]$ where x=1-6 is the Q23 item value as above.
The Q27 score = $100*[(6-x)/5]$ where x=1-6 is the Q27 item value as above.
The Q29 score = $100*[x/5]$ where x=1-6 is the Q29 item value as above.
The Q31 score = $100*[x/5]$ where x=1-6 is the Q31 item value as above.

The SF-36 vitality score is the average of the Q23, Q27, Q29 and Q31 scores. If at least two of the four questions have been answered, the SF-36 bodily pain score will be calculated.

22 Appendix 8: MedDRA Internationally Agreed Order for System Organ Class

The internationally agreed SOC order to be used for medical history and AE summary tables is provided in [Table 9](#).

Table 9 MedDRA Internationally Agreed SOC Order

Order Number	System Organ Class
1	Infections and infestations
2	Neoplasms benign, malignant and unspecified (incl cysts and polyps)
3	Blood and lymphatic system disorders
4	Immune system disorders
5	Endocrine disorders
6	Metabolism and nutrition disorders
7	Psychiatric disorders
8	Nervous system disorders
9	Eye disorders
10	Ear and labyrinth disorders
11	Cardiac disorders
12	Vascular disorders
13	Respiratory, thoracic and mediastinal disorders
14	Gastrointestinal disorders
15	Hepatobiliary disorders
16	Skin and subcutaneous tissue disorders
17	Musculoskeletal and connective tissue disorders
18	Renal and urinary disorders
19	Pregnancy, puerperium and perinatal conditions

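### Two SAP formulas for exploratory outputs are wrong as written: SE(log RR) for the apremilast comparison has no positive value under the root, and the SF-36 vitality score runs 10–110 instead of 0–100

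*SAP*

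**What the plan says.** **Relative risk.** SAP Section 9.6.2.1 defines N_A and N_P as the numbers evaluated in each arm, and n_A and n_P as event counts ("n_A = number of participants with event on active treatment", with the same for placebo). The relative risk is then (n_A/N_A)/(n_P/N_P), which makes sense only if n is a count. The standard error of log RR is the square root of a sum whose two fractions are printed as "1-n_A}{n_A N_A} + \frac{1-n_P}{n_P N_P". It feeds the 95% CI of the indirect relative risk.

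Section 9.6.2.3 applies this to three binary endpoints against UNVEIL (PASI-50, PASI-75, PGA 0 or 1). Section 9.6.2.4 adds one PGA endpoint against ADVANCE, with a condition: "This analysis will only be performed if these results are published prior to DB lock for this study". Section 9.6.2 labels all these comparisons descriptive, without p-values.

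**Vitality.** SAP Section 5.3.3.11 says the SF-36 scores follow the RAND algorithms as set out in Section 21 (Appendix 7). There Q23 and Q27 are scored 100 × (6 − x)/5. For the reverse-worded items the text reads "The Q29 score = $100*[x/5]$ where x=1-6 is the Q29 item value as above", and Q31 has the same form. The vitality score is the average of the four.

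The rule for partial answers appears twice. Section 5.3.3.11 says the vitality score "will be calculated if at least two of the two questions have been answered", although the score has four items. The vitality paragraph of Section 21 says "If at least two of the four questions have been answered, the SF-36 bodily pain score will be calculated", naming the wrong score.

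Absolute and percentage change in Pain and Fatigue scores are exploratory endpoints (Sections 4.2 and 9.6.1). For a participant with a zero baseline on these scales, Section 9.6.1 says "that participant will be excluded from any of the percentage change from baseline summaries and analyses".

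**The concern.** The standard-error expression has the form that is right for a proportion p, namely (1 − p)/(pN), but the symbols are defined as counts. A count of 1 or more makes each fraction zero or negative, so the root has no usable value. The same line serves both the EDP1815 and the apremilast components. It therefore affects nine planned intervals against UNVEIL (three endpoints × three doses; Tables 14.2.35.1.1 to 14.2.35.1.3), plus three against ADVANCE if that comparison is run (Table 14.2.35.2.1). A programmer who meets the failure has to choose a replacement that was not prespecified.

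The vitality error raises no such alarm. The code runs and most of its output looks reasonable. The reverse items sit 20 points too high, so a complete score sits 10 points too high. Percentage change, which divides by the baseline, is then misreported (Table 14.2.26), and the zero-baseline exclusion cannot operate on a complete score. A second programmer working from the same text would reproduce the error.

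**Working it through.** The SAP states no SE value and no vitality range, so there is no printed figure to reproduce. Both formulas are evaluated as written.

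**(a) SE(log RR)**

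Inputs: the formula and definitions in Section 9.6.2.1, and 50 participants per active dose and 75 pooled placebo from Section 6. The documents give neither responder counts nor the size of the subgroup matched to UNVEIL. The counts below are assumptions: 40%, 60%, 80% or 100% of 50 and 75 qualify, with about 30% and 16% responding.

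- As written, under the root: `(1 − n_A)/(n_A × N_A) + (1 − n_P)/(n_P × N_P)`
- Correct for counts, under the root: `1/n_A − 1/N_A + 1/n_P − 1/N_P`

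Worked case, 9/30 against 7/45:

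- As written: (1 − 9)/(9 × 30) + (1 − 7)/(7 × 45) = −0.0296 − 0.0190 = −0.0487.
- Correct: sqrt(1/9 − 1/30 + 1/7 − 1/45) = sqrt(0.1984) = 0.445.
- As written, but with n read as the proportions 0.300 and 0.156: also 0.445. This points to proportion notation combined with count definitions.

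| Active | Placebo | Under the root, as written | Correct SE |
|---|---|---|---|
| 6/20 | 5/30 | −0.068 | 0.532 |
| 9/30 | 7/45 | −0.049 | 0.445 |
| 12/40 | 10/60 | −0.038 | 0.376 |
| 15/50 | 12/75 | −0.031 | 0.342 |

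The failure does not depend on the assumed counts. For any n ≥ 1, (1 − n)/(nN) ≤ 0, with equality only at n = 1. Over all non-zero count pairs at the four sizes (600 + 1,350 + 2,400 + 3,750 = 8,100), none is positive and 4 are zero, namely n_A = n_P = 1 at each size.

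**(b) Vitality**

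- Q23 and Q27, 100 × (6 − x)/5 for x = 1 to 6: 100, 80, 60, 40, 20, 0.
- Q29 and Q31 as written, 100 × x/5: 20, 40, 60, 80, 100, 120.
- Q29 and Q31 on 0–100, 100 × (x − 1)/5: 0, 20, 40, 60, 80, 100.
- Four-item minimum as written: (0 + 0 + 20 + 20)/4 = 10. Maximum: (100 + 100 + 120 + 120)/4 = 110.
- Over all 6 × 6 × 6 × 6 = 1,296 answer patterns, the written score is exactly 10 above the 0–100 score. Five patterns exceed 100, and the single true-zero pattern scores 10.

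With complete answers at both visits the 10 cancels in absolute change. For percentage change, with B the true baseline:

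reported % change = true % change × B/(B + 10)

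| True baseline B | True change for +10 points | Reported |
|---|---|---|
| 20 | +50% | 10/30 = +33% |
| 40 | +25% | 10/50 = +20% |
| 60 | +16.7% | 10/70 = +14.3% |
| 0 | excluded under Section 9.6.1 | 10/10 = +100% |

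With partial answers the shift is 20 × (share of answered items that are Q29 or Q31). With at least two items answered it can be 0, 6.7, 10, 13.3 or 20. If a participant answers all four items at baseline and only Q23 and Q27 later, the shift goes from 10 to 0. The reported change is then −10 with no true change. The documents give no rate of partial completion.

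**The case against.** The strongest point against (a) is that it rests on where the fraction bars fall in one stacked equation read from a PDF by a program. A source such as (1 − n_A/N_A)/n_A is correct for counts, uses the same symbols, and could have been flattened into the form seen here. The relative-risk fraction just above, with its inner n_A/N_A, came through intact, so a drafting slip remains the likelier cause. The source page should still be checked first. If the error is real, it also cannot produce a wrong published interval, because the calculation fails at once. That lowers the stakes but leaves the plan without a usable formula.

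On (b), Section 5.3.3.11 names an external algorithm against which a programmer could check. It also says that the algorithm is detailed in Section 21, so those lines are what would be programmed. The error is not invisible either: Listing 16.2.6.11 would show item scores of 120 wherever Q29 or Q31 is answered 6. With complete answers, only percentage change is affected among the change summaries. The true-zero baseline is 1 pattern in 1,296, and distortion from partial answers depends on a completion rate nobody has stated. These points limit the consequence without removing it. The two wording slips in the partial-answer rule are minor, and the intent is recoverable.

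The replacement formula in (a) is itself undefined when an arm has no events, and Section 9.6.2.1 gives no rule for that. This is a separate gap.

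**Conclusion.** Both errors stand. Given the definitions in Section 9.6.2.1, no pair of non-zero event counts gives a positive value under the root. The planned binary indirect comparisons therefore have no valid SE or 95% CI; this is certain as the text reads, subject only to confirming the fraction bars on the source page. Section 21 puts a complete vitality score on 10–110, which multiplies percentage change by B/(B + 10) and lets a true-zero baseline escape the exclusion in Section 9.6.1. Absolute change is correct when the same share of reverse items is answered at each visit.

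The reach is limited to exploratory, descriptive outputs, with no effect on any primary or secondary analysis. The illustrative SEs rest on assumed counts and subgroup sizes; the sign of the quantity under the root and the 10–110 range do not. The corrections should be made before programming is final, chiefly because the vitality error can pass unnoticed.

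**What to change.** 1. **Section 9.6.2.1.** Check the equation on the source page. If it reads as here, replace it with SE(log RR) = sqrt(1/n_A − 1/N_A + 1/n_P − 1/N_P), keeping n as counts. A sentence on arms with no events would close the separate gap at the same time.
2. **Section 21 (Appendix 7).** Score Q29 and Q31 as 100 × (x − 1)/5.
3. **Sections 5.3.3.11 and 21.** State in both places that the vitality score is calculated when at least two of its four items are answered, and correct the score name in the vitality paragraph of Section 21.

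The cost is one-line edits to the SAP and the matching code. No new data are needed, and no primary or secondary analysis changes.
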